2.4 BASELINE EVALUATION

- 2.4.1 Research and clinical laboratory tests to be performed within 4 weeks of study entry and prior to starting therapy. Refer to section 5 for details on biospecimen collection and biomarker studies.
- 2.4.2 Peripheral Blood/Urine (see section 5)
 - 2.4.2.1 For storage and establishing a biobank (AppendixC in section [15](#))
 - 2.4.2.2 Flow cytometry and other assays (see section 5):
 - Phenotypic analysis of NK, NKT, and T cells
 - Phenotypic analysis of B cell subsets
 - Proliferation assays for human T cells (CD4 and CD8)
 - Functional NK cell analysis
 - Regulatory T cell and myeloid derived suppressor cell (MDSC) phenotype
 - Chemokine and cytokine assay
 - Selected tumor cell antigen targets
- 2.4.3 Bone Marrow (see section [5](#)). Bone marrow aspirate and biopsy will be used for histopathological evaluation, to determine the immunophenotyping of aberrant clonal plasma cells by multiparametric flowcytometry, CD 138+ and CD 138- fractions cell sorting with subsequent correlatives on both fractions, and the expression of CCRN by gene expression profiling and quantitative PCR.

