5.2 BIOMARKER STUDIES: METHODS

While it has been shown that lenalidomide-induced NK cell activation is IL-2 dependent, the specific subset of cells responsible for mediating this effect has not been clearly elucidated. To conduct a comprehensive evaluation of a range of immune cells in relation to lenalidomide maintenance therapy, we will include analyses of B-, T-, NK and NKT cells and important signaling cytokines.

- **Phenotypic analysis of PBMCs:** Patients' PBMCs will be FACS-sorted into NK cells (CD3⁻CD16⁺CD56⁺), CD4 (CD3⁺CD4⁺), and CD8 (CD3⁺CD8⁺) T-cell subsets. The percentage of T cells (CD4, CD8), NKT and NK cells will be determined by phenotypic analysis of peripheral blood mononuclear cells (PBMCs) stained for CD56, CD3, CD4, CD8, and CD16. To obtain total numbers per milliliter of peripheral blood, the percentage of CD4 T or NK cells will be multiplied by the total lymphocyte count.
- **Phenotypic analysis of B cell subsets:** B cell subsets will be analyzed by phenotypic analysis of PBMCs stained for CD19, CD38 CD45, CD27 and CD138.

- **Proliferation assay for human T cells (CD4 and CD8):** 100 μ l of PBMC (1 x 10^6 cells/ml) will be added to each well of a in a 96-well round-bottom plate. The plate is coated with 100 μ l anti-CD3 (OKT3; eBioscience) at a concentration of 10 μ g/ml. Incubate plate in a humidified 37°C, 5% CO₂ incubator. All cells are cultured in medium RPMI 1640 (Mediatech, Inc., Herndon, VA) supplemented with 10% heat inactivated human AB serum (Gemini Bio-Products, Woodland, CA); 100 units/ml penicillin and 100 μ g/ml streptomycin (Mediatech, Inc.); 2 mM L-glutamine (Mediatech, Inc.). Cells are incubated for 3 days. Proliferation will be assessed by [³H]thymidine (1 μ Ci [0.037 MBq] per well) (Perkin-Elmer, Boston, MA) incorporation pulsed on day 4 and quantified 18 hours later using a liquid scintillation counter (Wallac, Gaithersburg, MD). All experiments will be performed in triplicate.

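### The exploratory T-cell proliferation assay gives one bulk count per fixed number of unsorted PBMC, so it cannot report CD4 and CD8 separately and it moves with the T-cell share of PBMC.

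*Combined protocol and SAP*

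**What the plan says.** Section 5.2 heads the assay "Proliferation assay for human T cells (CD4 and CD8"), and the baseline list in 2.4.2.2 carries nearly the same label, "Proliferation assays for human T cells (CD4 and CD8"). The method adds 100 µl of PBMC at 1 x 10^6 cells/ml to each well of a plate coated with anti-CD3. The readout is thymidine "incorporation pulsed on day 4 and quantified 18 hours later using a liquid scintillation counter". On replication the plan says: "All experiments will be performed in triplicate".

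The assay bullet has no sorting step, no readout that distinguishes subsets, and no normalisation to T cells plated.

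Elsewhere in 5.2, the phenotyping bullet says that patients' "PBMCs will be FACS-sorted into NK cells" and into CD4 and CD8 subsets, and that cell percentages come from PBMC stained for CD3, CD4, CD8, CD16 and CD56. The NK function bullet specifies sorted NK cells as its effectors.

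On status, 1.1 lists NK function among the secondary objectives but does not list T-cell proliferation. Section 8.3 treats the additional functional analyses as exploratory, intended to supply data for later studies.

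**The concern.** There are two separate difficulties.

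1. **Label against readout.** The heading names two subsets. Anti-CD3 stimulates every CD3+ cell in the well (CD4, CD8 and CD3+ NKT cells together), and the counter returns one number. A gain in one subset and a loss in the other can cancel and look like no change. Section 5.2 opens by remarking that the cell subset behind lenalidomide's effect on NK cells is not established, so subset resolution is of evident interest.

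2. **Composition mixed with function.** The input is a fixed number of PBMC, so the number of T cells in the well is set by their share of PBMC. Section 1.2 cites reports that lenalidomide raises T, NKT and NK numbers. Unless these populations move in proportion, the share changes on treatment and carries the count with it. A paired comparison with baseline then cannot tell a change in response per cell from a change in the mix of cells plated.

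At stake is how interpretable an exploratory result is, and so its use to the later studies that 8.3 has in mind.

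**Working it through.** **The plan's own figure.** The only power statement (8.1) concerns the four cell counts: 28 patients, an effect of 0.67 SD, two-sided paired t-test at 0.013, power 80%. With 27 degrees of freedom and noncentrality 0.67 x √28 = 3.545, the noncentral t distribution gives 80.4% (80.0% at 0.0125). The figure reproduces. It does not cover the proliferation assay, so nothing below alters it.

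**Cells per well** (inputs from 5.2): 0.1 ml x 1,000,000 cells/ml = 100,000 PBMC, whatever their composition.

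**Can one count be split by subset?** Assume a 60:40 CD4:CD8 mix; the documents give none. Relative well signal = 0.6 x a + 0.4 x b, where a and b are the per-cell CD4 and CD8 responses relative to baseline.

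| a (CD4) | b (CD8) | Relative signal |
|---|---|---|
| 1.0 | 1.0 | 0.60 + 0.40 = 1.00 |
| 1.2 | 0.7 | 0.72 + 0.28 = 1.00 |
| 0.8 | 1.3 | 0.48 + 0.52 = 1.00 |

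Three different biological states give the same reading. The specific mix does not matter: one equation cannot determine two unknowns. Triplicate wells reduce noise but add no second equation.

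**How far does a change in share move the count?** Assume signal proportional to T cells plated and response per T cell unchanged. Relative signal = new share / old share. The shares are assumptions, since the documents give none.

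- 50% to 60%: 50,000 to 60,000 T cells per well; 0.60/0.50 = 1.20, or +20%.
- 50% to 40%: 50,000 to 40,000; 0.40/0.50 = 0.80, or -20%.
- A 10-point shift in either direction: 0.10/0.40 = 25% from a 40% baseline, down to 0.10/0.70 = 14.3% from a 70% baseline.

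**A case using a figure from the documents.** Section 1.2 cites NK cells rising from 2.20 to 3.90 x 10^5/mL under lenalidomide plus dexamethasone, an increase of 1.70 x 10^5/mL. Hold the T-cell count fixed and let P be total PBMC per mL before treatment (assumed). Relative T-cell share = P / (P + 1.70 x 10^5).

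| P (per mL, assumed) | Relative share | Change in signal |
|---|---|---|
| 1.0 x 10^6 | 1.00/1.17 | -14.5% |
| 1.5 x 10^6 | 1.50/1.67 | -10.2% |
| 2.0 x 10^6 | 2.00/2.17 | -7.8% |
| 2.5 x 10^6 | 2.50/2.67 | -6.4% |

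Here the count falls with no loss of T-cell function, and a real gain of similar size would be hidden.

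**Was sorting meant but left unsaid?** The NK bullet states that its effectors are sorted, and the phenotyping bullet describes CD4 and CD8 sorting. The proliferation bullet is detailed down to the serum supplier and the counter, and it says PBMC. Read together, these bullets indicate that unsorted cells are what the plan specifies.

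**The case against.** The strongest reply is that little depends on this assay. It is exploratory, it is not a listed objective, and no test or decision rests on it. That stands, and it limits the weight of the point.

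Several stronger readings are tempting and are not supported:

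- **That a rise will be reported as better T-cell function.** No section says how this assay will be analysed, interpreted or reported.
- **That the bias runs upward.** The primary endpoint is absolute counts, not share, and no document predicts a rising share. If all PBMC populations grow by the same factor, the share is constant and the second difficulty disappears. The one change quantified in Section 1.2 points downward, though it comes from combination treatment.
- **That the plan promises separate CD4 and CD8 results.** The protocol often writes T cells with the two subsets in brackets, so the heading may only name the responding cells. The label is then ambiguous rather than false, but it still needs clarifying.
- **That sorted fractions should be plated.** Section 1.2 describes Tregs and MDSCs as inhibiting T-cell activation. Sorting CD4 and CD8 cells removes MDSCs and accessory cells from the well and so answers a different question. Whole PBMC may be a deliberate choice.

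The same biology limits normalisation: dividing by T cells plated does not isolate response per cell if suppressor or accessory cells also change. The panel's denominator is also unsettled, because 5.2 multiplies the percentage by the total lymphocyte count. What remains after these objections is that the readout is bulk, its label suggests otherwise, and no adjustment for composition is stated.

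**Conclusion.** The point holds as a limited, inexpensive correction to a stated method. That one count cannot give separate CD4 and CD8 results follows from the design and needs no assumption. That the count moves with T-cell share also follows from the fixed PBMC input, but its size and direction are unknown. Illustratively, it is ±20% for a 10-point shift from a 50% share, and about -14.5% to -6.4% for the cited NK rise. These figures rest on assumed shares and PBMC totals, proportionality of signal to T cells plated and, in the NK case, a fixed T-cell count.

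A reader might infer that the primary count comparison is compromised. It is not: it uses flow cytometry counts and does not draw on this assay. The sample size, power and listed objectives are untouched.

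**What to change.** In 5.2 and 2.4.2.2:

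1. Label the result total (bulk) T-cell proliferation.
2. Report the raw thymidine count together with the count per CD3+ T cell plated, where CD3+ cells plated = 100,000 x the CD3+ percentage of PBMC from the same sample's flow panel.
3. State that this percentage is of the PBMC plated and not of lymphocytes, and confirm that the panel yields it.
4. State that the normalised value assumes rough proportionality and does not remove effects of Tregs, MDSCs or accessory cells.

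Plating sorted CD4 and CD8 fractions is not part of the required change.

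The cost is a small amount of extra analysis and one check of the flow denominator. CD3 staining is already in the panel, so no additional blood or assay is needed if the PBMC percentage is available.

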5.3 SAMPLE STORAGE, TRACKING AND DISPOSITION

5.3.1 Procedures for Collecting, Processing, and Storage of Bone Marrow biopsies

- See Appendix F
- Orders for bone marrow biopsies should be placed in the Clinical Research Information System (Clinical Research Center, NIH, Bethesda, MD). Samples will be ordered and tracked through the CRIS Screens. Should a CRIS screen not be available, the NIH form 2803-1 will be completed and will accompany the specimen and be filed in the medical record. Samples will not be sent outside NIH without IRB notification and an executed MTA.
- Bone marrow biopsies will be submitted in native condition to the NCI Laboratory of Pathology and handled according to routine procedures for diagnosis. Bone marrow core biopsies will be fixed and paraffin embedded for histological and immunohistochemical analysis and long-term storage. Bone marrow aspirates will be prepared according to routine procedures. Five to ten air-dried aspirate smears will be stored long-term.
- Materials for research studies will be documented on form NIH 2803-1.
- Initial processing of bone marrow aspirates for research will depend on the size of the aspirate. CD138 positive plasma cells will be isolated from a subset of these samples.
- For the purposes of storage, all research samples except stored serum and urine will be assigned a unique number and cataloged. Viable frozen cells will be stored in a temperature controlled, alarm secured nitrogen tank in the NCI Department of Hematopathology. Frozen bone marrow biopsies and processed biologic material (such as RNA and protein) will be stored at -80°C in a temperature-controlled, alarm-secured freezer. All research samples except stored serum will be stored in the Lymphoid Malignancies Branch lab. For questions regarding these samples, please contact [name] at [contact].
- Frozen specimens will be wrapped in aluminum foil labeled with the patient's name and accession number, put into a resealable polyethylene freezer bag, and stored in a liquid nitrogen freezer. The liquid nitrogen freezers are monitored daily for temperature variations. A FileMaker Pro database called HP Patient Information and Specimen Inventory is used for tracking the samples.

5.3.2 Procedures for stored serum, peripheral blood, and urine specimens:

- See Appendix C for processing and storage procedures for [name] lab.

Abbreviated Title: Revlimid maintenance for MM

Version Date: 01/06/2017

5.3.3 Procedures for Collecting, Processing, and Storage of Blood samples for biomarker studies

- See Appendix D for processing and storage procedures for [name] lab
- Batched blood samples for research purposes will be further analyzed for biomarker studies in [name] lab as per the methods detailed in section **5.1**

5.3.4 Protocol Completion & Sample Destruction

- The principal investigator will report destroyed samples to the IRB if samples become unsalvageable because of environmental factors (ex. a broken freezer or lack of dry ice in a shipping container) or if a patient withdraws consent. Samples will also be reported as lost if they are lost in transit between facilities or misplaced by a researcher. Freezer problems, lost samples, or other problems associated with samples will also be reported to the IRB, the NCI Clinical Director, and the office of the Center for Cancer Research of the NCI.

6 DATA COLLECTION AND EVALUATION

6.1 DATA COLLECTION

- Data will be prospectively collected and entered into the NCI C3D clinical trials database. All adverse events that are Grade 3 or higher related to lenalidomide and/or research procedures will be collected into the NCI C3D database. All data will be kept secure. Personal identifiers will not be used when collecting and storing data. An enrollment log will be maintained in the regulatory binder/file which is the only location of personal identifiers with unique subject identification number.

- When patients complete protocol treatment but remain on-study, the following data will be collected:
 - adverse events related to lenalidomide
 - survival status which will be collected by phone or clinic visit
 - additional cancer therapy received

- Record Keeping:

Complete records must be maintained on each patient; these records will consist of the hospital chart as well as any other information obtained from outside laboratories, radiology reports, or physician's records. These records will serve as the primary source material that forms the basis for the research record. All relevant data will also be entered on a computer database from which formal analyses are done. The primary source documentation will include patient eligibility data, patient history, flow sheets (including specialty forms for pathology, radiology, or surgery), an off-study summary sheet, and a final assessment by the treating physician.

- Forwarding of Patient Data from Other Institutions:

Either due to extenuating medical circumstances or for convenience, some patients may elect to have certain routine laboratory studies or protein marker analyses performed at an outside institution between scheduled interval visits to the CRC for this protocol. These results will be forwarded to the Myeloma Research Nurse who

will enter the data into the study database. Additional blood or tissue samples drawn on patients enrolled in this protocol between scheduled visits may be forwarded and entered into the database as well.

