3.3 DOSE MODIFICATIONS

Before each cycle, patients will be evaluated for possible toxicities that may have occurred after the previous dose(s). Toxicities will be assessed according to the NCI Common Terminology Criteria for Adverse Events (CTCAE) (<http://ctep.cancer.gov/reporting/ctc.html>). Each adverse event (AE) attributed to lenalidomide will be carefully recorded, so that the dose modifications can be made accordingly. If multiple toxicities are noted, the dose adjustments and/or delays will be made according to guidelines that address the most severe toxicity.

3.3.1 Dose reduction steps:

Abbreviated Title: Revlimid maintenance for MM

Version Date: 01/06/2017

Dose	Lenalidomide
Baseline dose	10 mg
One level dose reduction	5 mg
Two level dose reductions	5 mg every other day

3.3.2 Dose adjustments for Thrombocytopenia:

Thrombocytopenia	Recommended Course
First Episode- Platelet count $< 25 \times 10^9/L$	Hold lenalidomide. Hold prophylactic anti-coagulation. Monitor CBC weekly. Platelet count returns to $\geq 25 \times 10^9/L$. Resume lenalidomide at 10 mg. Resume prophylactic anti-coagulation, if no bleeding.
Subsequent Episodes- Platelet count $< 25 \times 10^9/L$	Hold lenalidomide. Hold prophylactic anti-coagulation. Monitor CBC weekly. Platelet count returns to $\geq 25 \times 10^9/L$. Resume lenalidomide at next lower dose level. Resume prophylactic anti-coagulation, if no bleeding. Do not decrease dose below 5 mg every other day.

*In case of thrombocytopenia, the decision to modify the dose of lenalidomide, administer platelet transfusions, and resume anti-coagulation may be based on the clinical judgement of the PI.

3.3.3 Dose adjustments for Neutropenia:

Neutropenia	Recommended Course
First episode- (Neutropenia is the only hematologic toxicity) ANC $< 0.5 \times 10^9/L$ (grade 4) ANC $< 1.0 \times 10^9/L$ (grade 3) with fever/sepsis	Hold lenalidomide. Consider growth factors. Monitor CBC weekly. ANC returns to $\geq 0.5 \times 10^9/L$, and fever/sepsis have resolved. Resume lenalidomide at same dose level, and consider stopping growth factors.

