6.3 TOXICITY CRITERIA

The following adverse event management guidelines are intended to ensure the safety of each patient while on the study. The descriptions and grading scales found in the revised NCI Common Terminology Criteria for Adverse Events (CTCAE) version 4.0 will be utilized for AE reporting. All appropriate treatment areas should have access to a copy of the CTCAE version 4.0. A copy of the CTCAE version 4.0 can be downloaded from the CTEP web site (http://ctep.cancer.gov/protocolDevelopment/electronic_applications/ctc.htm#ctc_40).

Attribution of the AE:

- Definite: The AE is clearly related to the study treatment.
- Probable: The AE is likely related to the study treatment.
- Possible: The AE may be related to the study treatment.
- Unlikely: The AE is doubtfully related to the study treatment.
- Unrelated: The AE is clearly NOT related to the study treatment.

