7 SAFETY REPORTING REQUIREMENTS/DATA AND SAFETY MONITORING PLAN

7.1 DEFINITIONS

7.1.1 Adverse Event

An adverse event is defined as any reaction, side effect, or untoward event that occurs during the course of the clinical trial associated with the use of a drug in humans, whether or not the event is considered related to the treatment or clinically significant. For this study, AEs will include events reported by the patient, as well as clinically significant abnormal findings on physical examination or laboratory evaluation. A new illness, symptom, sign or clinically significant laboratory abnormality or worsening of a pre-existing condition or abnormality is considered an AE. All AEs that are Grade 3 or higher must be recorded on the AE case report form.

All AEs, including clinically significant abnormal findings on laboratory evaluations, regardless of severity, will be followed until return to baseline or stabilization of event. Serious adverse events that occur more than 30 days after the last administration of investigational agent/intervention and have an attribution of at least possibly related to the agent/intervention should be recorded and reported as per section **7.2**.

An abnormal laboratory value will be considered an AE if the laboratory abnormality is characterized by any of the following:

- Results in discontinuation from the study
- Is associated with clinical signs or symptoms
- Requires treatment or any other therapeutic intervention
- Is associated with death or another serious adverse event, including hospitalization.
- Is judged by the Investigator to be of significant clinical impact
- If any abnormal laboratory result is considered clinically significant, the investigator will provide details about the action taken with respect to the test drug and about the patient's outcome.

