7.2.2 NCI-IRB Requirements for PI Reporting at Continuing Review

The protocol PI will report to the NCI-IRB:

1. A summary of all protocol deviations in a tabular format to include the date the deviation occurred, a brief description of the deviation and any corrective action.
2. A summary of any instances of non-compliance
3. A tabular summary of the following adverse events:
 - All Grade 3 and 4 events that are possibly, probably or definitely related to the research;
 - All Grade 5 events regardless of attribution;
 - All Serious Events regardless of attribution.

NOTE: Grade 1 and Grade 2 events are not required to be reported.

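### Sections 6.1 and 7.1.1 set different capture rules for Grade 3 or higher adverse events, so the analysis database can omit events judged unrelated

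*Combined protocol and SAP*

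**What the plan says.** Section 6.1 (Data Collection) sets the rule for the trial database: "All adverse events that are Grade 3 or higher related to lenalidomide and/or research procedures will be collected into the NCI C3D database". On the source of results it adds: "All relevant data will also be entered on a computer database from which formal analyses are done". For patients who have finished protocol treatment but remain on study, it lists "adverse events related to lenalidomide", with survival status and further cancer therapy.

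Section 7.1.1 (Adverse Event) defines an adverse event as one that counts "whether or not the event is considered related to the treatment or clinically significant", and then requires: "All AEs that are Grade 3 or higher must be recorded on the AE case report form".

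Section 7.2.2 (continuing review by the IRB) asks for a table with three scopes. Grade 3 and 4 events are included if at least possibly related. Grade 5 events are included without regard to attribution. The third scope is "All Serious Events regardless of attribution".

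Section 6.3 defines five attribution levels, from definite to unrelated. The middle one reads "Possible: The AE may be related to the study treatment". Section 3.3 has a further recording rule, tied to dosing: "Each adverse event (AE) attributed to lenalidomide will be carefully recorded, so that the dose modifications can be made accordingly".

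**The concern.** The same event can be in or out of the database depending on which section the data manager follows. Section 6.1 selects on relatedness, while 7.1.1 requires every Grade 3 or higher event on the form. No sentence says that unrelated events on the form are then entered in C3D, or that they are deliberately left out.

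What is at stake is any toxicity summary drawn from the database. In a single-arm trial, relatedness is judged by investigators who know the treatment and have no control group against which to check a background rate. If that judgement decides whether an event is entered, a later reader cannot recover the all-cause rate or see how the judgement was used. If it is only a field on an entered event, both remain possible.

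**Working it through.** There is no stated figure to reproduce. The check is a comparison of the rules.

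**Step 1. The rules side by side.**

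| Section | Destination | Grade | Attribution filter |
|---|---|---|---|
| 6.1 | C3D database | 3 or higher | Related to lenalidomide and/or research procedures |
| 6.1, after protocol treatment | Data collected on study | None stated | Related to lenalidomide |
| 7.1.1 | Adverse event case report form | 3 or higher | None |
| 7.2.2 | IRB table | 3 and 4 | Possibly, probably or definitely related |
| 7.2.2 | IRB table | 5 | None |
| 7.2.2 | IRB table | Any serious event | None |
| 7.2.4 | Manufacturer | Any serious event | None |

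The rows for 6.1 and 7.1.1 have the same grade threshold and differ on attribution. That is the conflict.

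**Step 2. Follow an on-treatment event judged unrelated through the rules.**

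- *Grade 5:* outside the 6.1 description, but on the form (7.1.1) and in the IRB table (7.2.2). Deaths other than from progressive disease also go to the IRB in expedited form (7.2.1).
- *Serious, Grade 3-4:* outside the 6.1 description, but on the form, in the IRB table and reported to the manufacturer (7.2.4).
- *Non-serious, Grade 3-4:* outside the 6.1 description and outside the IRB table. The case report form is the only place it is required.

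The third group is the most exposed. Anemia shows how it could arise: section 10.3 names it as a frequent complication of myeloma, and section 11.1.2 lists it among the most common reactions to lenalidomide (over 20%). A non-serious Grade 3 anemia put down to the disease would fall here.

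**Step 3. Is the filter defined?** Section 6.3 gives five levels and 6.1 points to none of them. Section 7.2.2 draws the line at possible, but only for its own Grade 3-4 table. Section 7.1.1 draws it there for serious events more than 30 days after the last dose. Neither line is stated to govern 6.1, so events rated unlikely, and perhaps possible, could be handled either way.

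**Step 4. Which planned analyses use these data?** Section 1.1 lists no safety objective. Section 8 specifies paired tests on four cell counts and Kaplan-Meier estimates of duration of response and progression-free survival. None takes adverse event records as input.

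**Step 5. Size.** The documents give no expected rate of Grade 3 or higher events judged unrelated, so the number omitted cannot be calculated. The effect per patient can be. With the 28 patients of section 8.1 as denominator, each patient whose only Grade 3 or higher event is left out lowers the observed all-cause proportion by 1/28 = 0.036, or 3.6 percentage points. Replacement of patients under section 3.1 would enlarge the denominator and shrink this slightly.

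**The case against.** The strongest reply is that the two sections govern different things. Section 6.1 does not use the word only, and 7.1.1 speaks of the form, not the database. Section 6.1 also says in general terms that data are entered in C3D and that relevant data go on a computer database. Read generously, everything on the form is entered and the related-events sentence just names one part of it. This is possible, so the database can omit unrelated events but need not. It does not settle the matter, because no sentence says so and the specific wording in 6.1 points the other way.

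It is also fair to say that no planned result is biased. A reader might infer that toxicity rates in this trial are understated, but the plan defines no such rate, so the risk concerns only summaries that may be produced later.

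A reader might further infer that second cancers would be lost, perhaps about half of them, because section 10.3 cites 7 to 8% on lenalidomide against 3 to 4% on placebo. The documents do not support this. Section 7.1.5 treats a new cancer during treatment as medically important under the serious-event definition, so it reaches the IRB table and the manufacturer whatever its attribution. The difference between two groups does not say how an investigator will rate one case, and 6.3 offers the possible category. The cited trials report 3- and 4-year survival, whereas patients here leave the study after two years of therapy and the 30-day visit (section 3.5.2.4).

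Nor does it follow that the IRB table cannot be produced. Section 7.2.2 does not require C3D as its source, and the forms and serious-event reports could supply it.

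**Conclusion.** The inconsistency is real and in the current text. Sections 6.1 and 7.1.1 give different capture rules for Grade 3 or higher events, the filter in 6.1 is undefined, and 7.2.2 needs events that the 6.1 description leaves out. Following 6.1 as written would produce a safety dataset selected by investigator attribution in a trial without a comparator.

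The consequence is moderate. Across all reporting channels the exposure falls mainly on non-serious Grade 3-4 events judged unrelated. The documents do not show how many there would be, or that C3D would in practice exclude them. The primary endpoints, progression-free survival and duration of response do not depend on the answer. The absence of blinding follows from the single-arm design and is not a separate fault; it only explains why attribution should not decide entry. The conclusion assumes that C3D, which 6.1 calls the clinical trials database, is the database that the same section says is used for formal analyses.

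**What to change.** Reword the sentence in section 6.1 so that all Grade 3 or higher adverse events are entered in C3D regardless of attribution, with the section 6.3 category recorded as a field. Any toxicity summary can then be given overall and by attribution, and 6.1 no longer needs a threshold for related. The same edit should say whether the narrower list for patients off protocol treatment is intended.

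The cost is a change of wording and modest extra data entry. Section 7.1.1 already requires these events on the case report form, so no new assessment is needed. Nothing in treatment, visits or sample size changes.
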